12.6 Secondary Objectives and Endpoints

12.6.1 Secondary Endpoint Analysis Variables

12.6.1.1 Nicotine Exposure Parameters for Fixed Puffing

Nicotine exposure parameters for fixed puffing be derived from plasma nicotine versus time data using a non-compartmental technique. In particular:

cC_{\max}	Background-corrected maximum plasma concentration
t_{\max}	Time to peak plasma nicotine concentration during fixed puffing product use, t_{peak} will be reported as long as there is at least one quantifiable concentration post-exposure
$cAUC_{(0-4h)}$	Background-corrected area under the concentration-time curve that is above the corrected baseline from the start of fixed puffing product use to 4 hours.

Additional plasma PK parameters may be derived and/or reported as appropriate.

More details on nicotine PK parameter derivations will be provided in the SAP.

12.6.2 Statistical Analysis

Nicotine plasma PK parameters will be determined from the plasma concentration-time profiles for all evaluable subjects according to conventional NCA methods. Actual sampling times, rather than scheduled sampling times, will be used in all computations involving sampling times. For the fixed puffing regimen, background-corrected nicotine plasma concentrations will be used for the estimation of plasma PK parameters by NCA. Plasma PK parameters will be summarized using descriptive statistics by study product (i.e., subjects' own e-cigarette or P4M3 variant), as appropriate.

For the fixed puffing regimens, the ratio of geometric mean nicotine exposure normalized $cAUC_{(0-4h)}$ and cC_{\max} for each P4M3 variant in reference the subject's own e-cigarette will be presented with associated 90% CIs. The theoretical nicotine exposure, as appropriate, will be used for the purposes of parameter normalization.

In order to evaluate the PK parameters of the P4M3 variants with subjects' own e-cigarette, an ANOVA will be conducted on logarithmically transformed $cAUC_{(0-4h)}$, cC_{average} , and cC_{\max} , as applicable. The model will include sex and product use as fixed effects and subjects as a random

Data and information contained in this document are considered to constitute trade secrets and confidential commercial information, and the legal protections provided to such trade secrets and confidential information are hereby claimed under the applicable provisions of US law. No part of this document may be publicly disclosed without the written consent of PMI.

effect. For each P4M3 variant, the geometric LSM P4M3 variant:e-cigarette ratios will be presented with 90% CIs. The dose-proportionality of the e-liquid concentrations (with lactic acid only) versus nicotine exposure PK parameters will be investigated graphically on an exploratory basis.

In addition, the impact of the lactic acid will be evaluated for the PK parameters, using an ANOVA on logarithmically transformed $cAUC_{(0-4h)}$ and cC_{max} , adjusting for sex, with sequence, subject nested within sequence, period, and product as fixed effects. The geometric LSM P4M3-1.7%LA:P4M3-1.7% ratios will be presented with 90% CIs. Wilcoxon signed-rank test will be used to compare t_{max} between the study products.

12.6.2.1 VAS Craving Assessments

VAS craving assessments will be summarized by product and product use period. VAS craving assessments that are collected during the product use periods will be summarized over time within each product use period. The scores will be assessed using repeated measures ANCOVA with product use, sex, baseline value, the interaction of product and time point, and time point as fixed effects including the assessment time points as repeated measurements. The interaction term will be removed if $p > 0.1$. Additionally, the VAS craving score will be analyzed as AUC (similar to the calculation of $AUC_{(0-4h)}$, averaged over the total time) for each product use period and analyzed using the same model as for the nicotine exposure parameters.

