In order to evaluate the PK parameters of the P4M3 variants with subjects' own e-cigarette, an ANOVA will be conducted on logarithmically transformed $cAUC_{(0-4h)}$, $cC_{average}$, and cC_{max} , as applicable. The model will include sex and product use as fixed effects and subjects as a random effect. For each P4M3 variant, the geometric least-squares means (LSM) P4M3 variant:e-cigarette ratios will be presented with 90% CIs. The dose-proportionality of the e-liquid concentrations (with lactic acid only) versus nicotine exposure PK parameters will be investigated graphically on an exploratory basis.

In addition, the impact of the lactic acid will be evaluated for the PK parameters, using an ANOVA on logarithmically transformed $cAUC_{(0-4h)}$ and cC_{max} , adjusting for sex, with sequence, subject nested within sequence, period, and product as fixed effects. The geometric LSM P4M3-1.7%LA:P4M3-1.7% ratios will be presented with 90% CIs. Wilcoxon signed-rank test will be used to compare t_{max} between the study products.

Pharmacodynamic Analysis:

PD will be summarized by study product.

- VAS craving assessments will be summarized over time within each of the fixed puffing regimen and *ad libitum* use. The scores will be assessed using an Analysis of Covariance (ANCOVA) model with product use, sex, baseline value prior to product use, and the interaction of product and time point as fixed effects and subjects as random effect including the assessment time points as repeated measurements. The interaction term will be removed if $p > 0.1$. The summary statistics will include least square means as well as arithmetic means. Additionally, the VAS craving score will be analyzed as AUC (similar to the calculation of $AUC_{(0-4h)}$, averaged over the total time of VAS collection period) and analyzed using the same model approach as for the PK parameters.
- Adapted mCEQ subscale scores and SQ answers will be summarized with descriptive statistics and displayed graphically by product. The scores/answers will be analyzed using an ANOVA adjusted for sex with product use as a fixed effect and subjects as a random effect. HPT parameters will be summarized by product use period with geometric means, % coefficient of variation (CV), and 90% CIs.

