7.7.3 Visual Analogue Scale for Craving

The VAS craving will be completed by the subject himself/herself. The first assessment will be done prior to T0 of each fixed puffing regimen and *ad libitum* use on Days -1 to 4. All other assessments will be done after T0, at 4 minutes \pm 2 minutes, at 10 minutes \pm 2 minutes, at 15 minutes \pm 2 minutes, 30 minutes \pm 5 minutes, 1 hour, 2 hours, 4 hours on each of Day -1 to Day 4.

The questionnaire will be reviewed for completeness by the study site study collaborator and subjects will be requested to complete any missing information.

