**Table 8. Event Schedule – Fixed Puffing and *Ad Libitum* Product Use with P4M3 Variants (Days 1 to 4)**

Blood sample	Procedures	Additional information
	Optional morning snack	
	Randomization (Day 1 only)	Sequence 1: P4M3-1.7%; P4M3-1.7%LA; P4M3-3%LA; and P4M3-4%LA Sequence 2: P4M3-1.7%LA; P4M3-1.7%; P4M3-3%LA; and P4M3-4%LA
√	Nicotine baseline plasma sampling prior P4M3 variants use	One blood sample will be taken prior to the start of product use (T0): 15 minutes ± 5 minutes (T-1).
√	Clinical laboratory parameters (hematology, urine analysis, clinical chemistry) (Day 2 only)	Fasting state
	Vital signs prior product use	At least 5 minutes in supine position prior to measurement
	VAS for craving prior product use (x1 T0)	
	Washout	Minimum of 10 hours
	Fixed puffing P4M3 variants with HPT	Fixed puffing regimen comprising of 12 puffs in total at a rate of one puff every 30 seconds (± 5 seconds)
√	Plasma samples for nicotine	Post T0, blood will be drawn at the following time points: T1 after 2 minutes ± 30 seconds, T2 after 4 minutes ± 1 minute, T3 after 7 minutes ± 1 minute, T4 after 10 minutes ± 1 minute, T5 after 15 minutes ± 2 minutes, T6 after 30 minutes ± 2 minutes, T7 after 1 hour ± 5 minutes, T8 after 2 hours ± 5 minutes, T9 after 4 hours ± 5 minutes.

VAS Craving assessment	Post T0, VAS assessments will be assessed at the following time points 4 minutes (± 2 minutes) 10 minutes (± 2 minutes) 15 minutes (± 2 minutes) 30 minutes (± 5 minutes) 1 hour (± 10 minutes) 2 hours (± 10 minutes) 4 hours (± 10 minutes)
SQ assessment	Within 60 minutes after completion of product use
Assessment of cough (VAS, three Likert scales and one open question)	Completed by the subject on site within 30 minutes of product use
Vital signs	At least 5 minutes in supine position prior to measurement, to be conducted at 60 minutes ± 10 minutes post end of product use
Device events malfunctions/misuse	As reported post product use
Washout	Minimum 10 hours
Lunch	
Vital signs pre-product use	At least 5 minutes in supine position prior to measurement
VAS for craving prior product use (x1 T0)	
√ Nicotine baseline plasma sampling (x1 T0) prior P4M3 variants ad libitum use	One blood sample will be taken prior to P4M3 variants ad libitum use (T0): 15 minutes ± 5 minutes (T-1)
Ad libitum use P4M3 variants with HPT	Ad libitum use for 60 minutes (± 5 minutes) with HPT recording

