12.1.1 Definitions for Statistical Data Analysis

Unless otherwise stated, for the purposes of statistical analyses, baseline is defined as the last available time point prior to T0 on Day -1.

Nicotine exposure parameters will be derived from plasma nicotine versus time data by NCA using Phoenix WinNonlin, Version 7.0 or higher. C_{max}, AUCs, and related PK parameters, as appropriate, will also be calculated. To minimize the potential bias in the nicotine plasma PK parameters for the fixed puffing regimens, background-concentration correction will be applied to the concentration data and derived PK parameters to adjust for carry-over effects. For nicotine exposure parameters, baseline (C₀) will be defined as the concentration immediately prior to T0 for each session. The baseline correction will be implemented by calculating the nicotine exposure parameters using adjusted concentration values as described below:

The nicotine terminal elimination rate constant λ_z (and $t_{1/2z}$) will be estimated from the Day 5 PK samples (or early termination samples, if available) using a linear regression on the log concentration the pre-T0 time points. The regression analysis should contain data from at least 3 different time points in the terminal phase (including the last quantifiable concentration but excluding the concentration at t_{max}), consistent with the assessment of a straight line on the log-transformed scale. The nicotine plasma background-corrected PK parameters will be derived by performing the NCA on the corrected concentrations.

For the purposes of background-correction of the plasma concentrations post-baseline the following formula will be applied: $cC_t = C_t - C_0 * e^{-\lambda_z t}$. Where, C_t is the corrected concentration at each time point, C_0 is the pre-use baseline concentration, λ_z is the Day 5 (or early termination, if available) terminal elimination rate constant and t is the actual time.

If plasma concentrations cannot be background-corrected in a sufficient number of subjects e.g., in the event that the λ_z (or $t_{1/2z}$) cannot be estimated, modelling approaches may be applied including conventional compartmental analyses. The total (untransformed) PK parameters will be reported and used for statistical analyses instead in case both correction methods are unsuccessful. If warranted, nonlinear mixed-effect modeling using nicotine pooled data across studies may also be used.

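### The protocol gives the baseline covariate of the VAS craving ANCOVA in two ways, and the Section 12 reading (Day -1 value) does not adjust product contrasts for pre-session craving

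*Protocol*

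**What the plan says.** Three places bear on the covariate.

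- **Section 12.6.2.1:** "The scores will be assessed using repeated measures ANCOVA with product use, sex, baseline value". The product-by-time interaction and time point follow as further fixed effects. The baseline is not qualified, and no subject random effect is listed.
- **Section 12.1.1:** "Unless otherwise stated, for the purposes of statistical analyses, baseline is defined as the last available time point prior to T0 on Day -1". For nicotine the same section departs from this default: baseline "will be defined as the concentration immediately prior to T0 for each session". It has no matching sentence for the VAS.
- **Synopsis, Pharmacodynamic Analysis:** the same VAS model, with "product use, sex, baseline value prior to product use" among its terms and subjects as a random effect.

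The score needed for a session baseline exists. Section 7.7.3 says "The first assessment will be done prior to T0 of each fixed puffing regimen", and applies the same to *ad libitum* use, on Days -1 to 4.

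**The concern.** A statistician who follows Section 12 alone would enter one Day -1 score per subject and regimen. That is the true pre-use score only for the own e-cigarette. For the P4M3 variants it is one to four days old.

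The design makes the choice matter. Own product is always used on Day -1, 3%LA always on Day 3 and 4%LA always on Day 4. Only the two 1.7% variants cross over, and the VAS model has no day or period term. Section 4.2 accepts a washout of at least 10 hours where it says about 3 days would be needed for full nicotine washout. Any drift in pre-use craving during confinement therefore runs along with product order. Under the Day -1 covariate, that drift would be read as a difference between the variants and the own e-cigarette.

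**Working it through.** **Inputs from the protocol.** Five products on five consecutive days (Day -1, Days 1 to 4), so 4%LA is used 4 days after the own product. Seven post-T0 VAS readings per session. Fixed puffing and *ad libitum* use are analysed separately (12.1.2). Sixteen subjects are randomized so that 12 remain after up to 25% with incomplete data: 12 / (1 - 0.25) = 16, which reproduces. The protocol states no VAS mean, SD, slope or drift, so there is no VAS figure to reproduce and everything below on size is assumed.

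**Step 1, algebra.** Let B_i be the Day -1 score of subject i, B_ip the score before the session with product p, and b the slope of post-use on pre-use craving. In the within-subject difference between product p and own product:

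- the Day -1 covariate contributes b × (B_i - B_i) = 0;
- the session covariate contributes b × (B_ip - B_i), because on Day -1 the two definitions coincide.

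With complete data the Day -1 covariate therefore gives the same product contrast as no baseline covariate at all.

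**Step 2, size.** Without adjustment, bias ≈ slope × drift per day × days since Day -1. For 4%LA against own product, with an assumed slope of 0.5:

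| Assumed drift (mm/day) | Calculation | Bias (mm) |
|---|---|---|
| 0 | 0.5 × 0 × 4 | 0 |
| 2.5 | 0.5 × 2.5 × 4 | 5 |
| 5 | 0.5 × 5 × 4 | 10 |

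For 3%LA (3 days) the last two rows become 3.75 and 7.5 mm. The sign follows the direction of the drift.

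**Step 3, simulation.** 16 subjects, 5 products, 7 readings per session, 150 replicates. Assumed: true product effect 0, pre-session mean 10 points lower on Day 4 than on Day -1, slope 0.6, between-subject SD 15, session SD 12, residual SD 8. The expected bias without adjustment is 0.6 × (-10) = -6.0. The table shows the mean contrast of the Day 4 product minus own product in a model with a random subject effect:

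| Covariate | Complete data | 4 of 16 subjects missing one product |
|---|---|---|
| None | -6.03 | -5.942 |
| Day -1 value | -6.03 | -5.943 |
| Pre-session value | +0.03 | -0.04 |

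With complete data the first two rows agree in every replicate to within 9e-14. With missing sessions, single datasets differ by up to 0.17 with a subject random effect and by up to 1.92 in ordinary least squares without one. The average imbalance stays unadjusted in both.

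**The case against.** The strongest reply is that the protocol already has the right covariate. Section 12.1.1 sets only a default, and it does not say that exceptions must stand in 12.6.2.1. The synopsis qualifies the covariate for this very model, and Table 8 labels the score on Days 1 to 4 in almost the same words ("VAS for craving prior product use (x1 T0"). This stands in part. A reader might infer from Section 12 that the protocol has settled on the Day -1 value; the documents do not support that. They support a conflict between synopsis and body text. The conflict still needs repair, because Section 12.1.1 writes out a per-session baseline where it wants one, and does so only for nicotine. Further detail is deferred to the SAP, but a SAP author who follows Section 12 would carry the Day -1 definition forward.

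The second reply concerns size, and it stands. The millimetre figures are assumptions multiplied out. Zero or small drift is plausible: each fixed-puffing session follows at least 10 hours without nicotine, and T0 is held to the same clock time within 30 minutes.

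The third reply also stands. A reader might infer from the simulation that the session covariate removes the bias entirely. That result is built in, since the drift was made to act only through a perfectly measured pre-use score. If the single reading had a within-subject reliability of, say, 0.7, about (1 - 0.7) of the bias would remain: 1.5 to 3 mm of the 5 to 10. Day effects that do not show in pre-use craving stay confounded with product whatever the covariate.

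Finally, product summaries over time and the pre-T0 scores would let a reader see a drift, though not adjust for it.

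**Conclusion.** The point holds as an inconsistency with a practical consequence. The synopsis and Section 12 specify different covariates for one model, and the literal Section 12 version does not adjust product contrasts for pre-session craving. The equivalence to having no covariate is exact with complete data and holds on average with the missingness simulated.

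The size is unknown. It runs from 0 without drift to about 5 to 10 mm for 4%LA against own product under the assumed slope of 0.5 and drift of 2.5 to 5 mm per day. Confidence is high for the textual conflict and the algebra, and low for any particular figure.

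VAS craving is one of several secondary pharmacodynamic endpoints, and Section 3.3 states that no hypothesis is tested. The impact is modest, but the correction is worth making.

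**What to change.** In Section 12.6.2.1, name the covariate as the VAS craving score taken just before T0 of the same session, and list subject as a random effect. Both agree with the synopsis. Keep the time-point main effect that 12.6.2.1 already has. The score is scheduled before every session on Days -1 to 4, so the change costs a few words and no new data. The study report should add that product and study day remain confounded for own e-cigarette, 3%LA and 4%LA, so that the adjusted contrasts are not read as free of day effects.

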12.6.2.2 Questionnaires (Adapted mCEQ and SQ)

Adapted mCEQ subscale scores and SQ answers will be summarized by product and product use period with descriptive statistics and displayed graphically. The scores/answers will be analyzed using an ANOVA adjusted for sex with product use, product, and time point as a fixed effect and subjects as a random effect.

12.6.2.3 Puffing Topography

HPT parameters ([Appendix 4](#)) will be summarized by product use period with arithmetic means, %CV, and 90% CIs. In order to evaluate the association between the HPT and the nicotine exposure, HPT parameters will be plotted against the nicotine exposure parameters with product indicated using different symbols for each nicotine concentration.

12.6.3 Safety Endpoints

In general, all safety data will be listed and tabulated using the approach described in [Section 12.1.2](#). Safety variables collected during exposure periods will also be reported by product exposure.

AE data will serve as the primary assessment of safety. Other safety variables monitored in this study include: respiratory symptoms (cough assessment VAS and Likert scales); vital signs (systolic and diastolic blood pressure, pulse rate, respiratory rate); spirometry; ECG data; clinical chemistry, hematology, and urine analysis safety panel; physical examination.

Data and information contained in this document are considered to constitute trade secrets and confidential commercial information, and the legal protections provided to such trade secrets and confidential information are hereby claimed under the applicable provisions of US law. No part of this document may be publicly disclosed without the written consent of PMI.

All AEs will be summarized by nicotine concentration (fixed puffing and *ad libitum* use combined) and overall. The number and percentage of subjects with AEs, SAEs, and device events will be tabulated by system organ class and preferred term. Summaries will also be presented for AEs leading to discontinuation, AEs leading to death, AEs by relatedness to product exposure (with and without laboratory related AEs), AEs by severity, and laboratory AEs. Tabulations will be performed for both the number of subjects experiencing an event and the number of events. Due to the laboratory schedule in this study, any lab related AEs will be assigned to P4M3 4% nicotine concentration.

Summary tables showing actual values and change from baseline of clinical findings will be provided for spirometry, ECGs, vital signs, and laboratory parameter. Descriptive statistics will be summarized by fixed puffing/*ad libitum* use and nicotine concentration and change from baseline will be presented for laboratory parameters, ECG, respiratory symptoms, and vital signs. Shift tables will be provided for laboratory and safety ECG data.

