In order to evaluate the association between the HPT and PK parameters, HPT parameters will be plotted separately for fixed puffing and *ad libitum* use against the PK parameters with study product indicated using different symbols for each nicotine concentration level.

In order to evaluate the association between the theoretical nicotine exposure and PK parameters, theoretical nicotine exposure will be plotted separately for fixed puffing and *ad libitum* use against the PK parameters with product indicated using different symbols for each nicotine concentration level.

Safety analysis:

The safety population will comprise all enrolled subjects. Adverse events will serve for the primary assessment of safety data. All safety data will be listed however only P4M3 variants-emergent AEs will be summarized by product variant (fixed puffing regimen and *ad libitum* use will be combined at the product variant level) and P4M3 overall. Other safety measurements (vital signs, etc.) will be summarized per fixed puffing regimen/*ad libitum* use and product.

Sample Size:

The sample size is empirically based, as there is no prior information on which to base the sample size and there is no consideration for statistical hypothesis. A sample of 12 subjects is targeted for the analysis of this study to obtain the precision about the mean and variance for the study objectives. Therefore, in order to ensure 12 subjects completing the study, 16 subjects will be randomized.

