6 INVESTIGATIONAL PRODUCTS

6.1 P4M3

6.1.1 Description

The P4M3 will be provided by the Sponsor and its distribution will be controlled by a qualified and appropriately trained designee. P4M3 with e-liquid contains the following concentrations of nicotine with and without lactic acid: 1.7 % nicotine without lactic acid, 1.7 % nicotine with lactic acid, 3 % nicotine with lactic acid, and 4 % nicotine with lactic acid.

P4M3 comprises the following components:

- A Battery (and electronics) Unit, onto which the Cartomizer is mounted.
- A disposable Cartomizer, which contains porous materials, a heater, and the nicotine solution (e-liquid).
- A USB cable to charge the Battery unit from a low voltage port.

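### Section 12.6.3 groups safety summaries by nicotine concentration and the synopsis by product variant; read literally, Section 12.6.3 merges 1.7% with 1.7%LA

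*Protocol*

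**What the plan says.** Two places in the protocol set the grouping of the safety tables.

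- **Section 12.6.3 (Safety Endpoints).** For AEs: "All AEs will be summarized by nicotine concentration", with the two regimens combined, and overall. For other safety data: "Descriptive statistics will be summarized by fixed puffing/*ad libitum* use and nicotine concentration". Near its start the section adds a general sentence: "Safety variables collected during exposure periods will also be reported by product exposure".
- **Synopsis, Safety analysis.** For AEs: "only P4M3 variants-emergent AEs will be summarized by product variant", with the two regimens combined, plus P4M3 overall. For the rest: "Other safety measurements (vital signs, etc.) will be summarized per fixed puffing regimen/*ad libitum* use and product".

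Section 6.1.1 lists the variants: "1.7 % nicotine without lactic acid, 1.7 % nicotine with lactic acid, 3 % nicotine with lactic acid, and 4 % nicotine with lactic acid". Section 6.3.3 gives two sequences that differ only in the order of the two 1.7% variants on Days 1 and 2. In both, 3%LA is used on Day 3 and 4%LA on Day 4, and each day has one variant for both regimens.

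**The concern.** The two rules produce different tables, because two of the four variants have the same nicotine concentration. A programmer who follows Section 12.6.3 would build three P4M3 columns; one who follows the synopsis would build four. The scope differs as well: Section 12.6.3 covers all AEs, the synopsis only those emergent on P4M3 variants.

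The merged pair is the one the randomisation exists to cross over, and it differs only in lactic acid. Section 2.2 names the presence of lactic acid as part of what the study evaluates, and Section 2.1.1 says it may reduce perceived harshness. Tolerability and cough are therefore outcomes on which the two 1.7% variants could differ.

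The merged column also covers twice the product days of the other two. Section 12.6.3 tabulates the number and percentage of subjects with AEs, and that percentage does not adjust for time at risk. In a concentration-ranging study, a raised percentage at the lowest concentration could mask a concentration trend or appear to reverse it.

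**Working it through.** The protocol gives no AE rate, so there is no planned figure to reproduce. The check has three steps.

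**1. The two rules side by side**

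| Item | Section 12.6.3 | Synopsis |
|---|---|---|
| Which AEs | all | P4M3 variant-emergent only |
| AE columns | nicotine concentration, overall | product variant, P4M3 overall |
| Other safety measurements | regimen and nicotine concentration | regimen and product |

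**2. Exposure per column**

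Inputs: the sequences in Section 6.3.3; 16 randomised and 12 targeted for analysis (Section 12.2).

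- Sequence 1 by concentration: 1.7% on Days 1 and 2, 3% on Day 3, 4% on Day 4.
- Sequence 2 by concentration: the same.
- With 16 subjects: 16 × 2 = 32 subject-days at 1.7%, against 16 × 1 = 16 at 3% and 16 at 4%.
- With 12 subjects: 24, 12 and 12.
- By variant, each of the four columns has 16 subject-days (or 12).

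The Day -2 product test, which uses P4M3-1.7%, is left out of these counts.

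**3. Effect on the percentage of subjects with an AE**

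Let p be the probability that a subject has at least one AE on a product day. Assume p is the same for every product; its value is an assumption. A one-day column shows p. The two-day column shows:

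- 1 − (1 − p)² if the two days are independent within a subject;
- p if the same subjects have AEs on both days.

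| Assumed p | 3%LA and 4%LA columns | Pooled 1.7%, same subjects | Pooled 1.7%, independent days | Ratio under independence |
|---|---|---|---|---|
| 0.10 | 10% | 10% | 1 − 0.90² = 19% | 1.9 |
| 0.20 | 20% | 20% | 1 − 0.80² = 36% | 1.8 |
| 0.30 | 30% | 30% | 1 − 0.70² = 51% | 1.7 |

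At p = 0.20 with 16 subjects, independence gives an expected 16 × 0.36 = 5.76 subjects in the pooled column, against 16 × 0.20 = 3.2 in each other column, although no product differs from another.

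This applies to subject-level AE incidence. A mean of vital signs is not raised by averaging over two days.

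**The case against.** The strongest reply is that pooling was never intended. The protocol often uses concentration as a label for the variants: Section 6.1.1 and the synopsis (Study Design and Investigational Products) each list all four products under that word. Section 12.6.3 itself assigns laboratory AEs to the 4% nicotine concentration, meaning the 4%LA variant. No sentence says that the two 1.7% products will be combined. The same section also promises reporting by product exposure for safety variables collected in the exposure periods, and all safety data are to be listed.

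Much of this stands, and it rules out three stronger readings that a reader might infer.

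- **That the lactic acid safety contrast is lost to the trial.** It is hidden only in the tables built by concentration. The product-exposure sentence and the listings keep it recoverable.
- **That the subjects' own e-cigarettes would be split by their various concentrations, or could not be compared.** No text says so. The synopsis summarises session measurements by product, which includes the own e-cigarette, and deliberately limits the AE summaries to P4M3-emergent events. A separate own-product AE column would be a preference; its absence is not an error.
- **That the lowest concentration will look worst.** This needs a roughly flat concentration response and AEs that do not simply recur in the same subjects. The percentages above rest on assumed rates.

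The objection does not remove the conflict. The general sentence says that by-product reporting will also be done; it does not replace the specific rules for the AE tables and descriptive statistics, and those say concentration. Nor is this detail simply left to the SAP: the protocol fixes the grouping twice, in different terms.

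**Conclusion.** The point holds as an inconsistency with a practical consequence. Section 12.6.3 and the synopsis disagree on the grouping of AEs, on the grouping of other safety measurements, and on which AEs are summarised. Taken literally, Section 12.6.3 merges the two crossed-over variants into a column with twice the product days of each of the others, and those tables then cannot show a lactic acid effect.

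The distortion of AE incidence is conditional. At assumed daily rates of 10, 20 and 30%, equal across products, it runs from none under full recurrence in the same subjects to 9, 16 and 21 percentage points under independent days (19 − 10, 36 − 20, 51 − 30). Positive within-subject correlation short of full recurrence falls in between.

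The disagreement itself rests only on the text and needs no assumption. Whether pooling was intended cannot be settled from the protocol, and its loose use of the word suggests it may not have been.

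**What to change.** In Section 12.6.3:

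- **AEs:** replace nicotine concentration with product variant, giving columns 1.7%, 1.7%LA, 3%LA, 4%LA and P4M3 overall.
- **Session-based measurements (vital signs, cough):** replace nicotine concentration with product, by regimen, including the own e-cigarette, as the synopsis has it.
- **Scope:** state in both places whether the summaries cover all AEs or only P4M3 variant-emergent AEs.

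ECG and spirometry are taken only at Screening and Discharge (or early termination), and the safety laboratory only at Screening, Day -2, Day 2 and Discharge (or early termination). Neither wording gives these a full set of product columns, so the change of term should not be extended to them as if it did.

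The cost is a text correction and table shells. No new data, visits or analyses are needed.
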